#### Investigations (Routinely performed for persistent diarrhoea patients at ICDDR,B)

1. Blood for CBC, electrolytes, albumin
2. Stool for M/E, Sudan III, helminths and parasites by formal ether concentration, and cryptosporidium
3. Stool for pH and reducing substances, electrolytes and osmolality.

4. Stool for C/S - Campy., Cholera, Shigella, Salmonella and ELISA for Rotavirus. E. coli colonies will be saved and tested for ETEC, EPEC and EAEC; Klebsiella strains will be saved for further evaluation.
5. \* Small intestinal intubation for collection of small intestinal fluid for quantitative microbiology and microscopy (for G.lamblia, cryptosporidium and S.stercoralis).
6. \* Lactose breath hydrogen test : for detecting lactose malabsorption.
7. Urine       ] if required  
       X-ray       ]  
       Blood C/S ]

#### Special investigations

1. \* Urinary BT-PABA test : as a non-invasive method of estimating pancreatic function.
2. \* Determination of Plasma secretin and Cholecystokinin (CCK) : to see whether the release of these two hormones (necessary for normal pancreatic function) from the intestinal mucosa, in response to food stimulation, is diminished.
3. \* Intestinal permeability test : as measured by differential absorption/excretion of lactulose and mannitol after a test dose. This non-invasive method is used to assess intestinal function. This test will be performed on admission, and after 7 days to assess change in intestinal function.

(The indication, method, and interpretation of the investigative tests marked [\*] are described in the appendix).

#### Balance study

The study diet will be continued, as started on 2nd day. The amount of diet provided to each patient will be 200 ml/kg/24 hour. At the 48th hour of admission, the first marker as charcoal tablet will be given. A 2nd charcoal marker will be given after 72 h at the same time of first marker. Time of appearance of first marker in stool will be taken as 0 h.

Collection of stool and urine will be started with the appearance of the first marker until 2nd marker comes out. 5 ml of acetic acid will be given in the collecting buckets. 72 h dietary intake will be measured and recorded. All vomitus will be collected in the same way. These samples will be kept at -20°C. Aliquotes of stool samples from homogenized 72 h collection will be taken and analysed for fat, nitrogen, and carbohydrates by subtracting those from total energy. Total energy content will be determined by calorimetry. Dietary and breast milk contents for fat, CHO and N will also be analysed. Total urinary N2 excretion/daily will be determined.

$$\text{Absorption coefficient} = \frac{\text{Intake} - \text{loss}}{\text{intake}} \times 100$$

Composition of diets/l

	Diet A	Diet B
Ground chicken meat	150.0 g	150.0 g
Glucose	20.0 g	20.0 g
Coconut oil	35.0 g	-
Soyabean oil	-	35.2 g
NaCl	1.0 g	1.0 g
Calcium lactate	0.5 g	0.5 g
MgCl 2	0.2 g	0.2 g
H 2 O upto	1.0 l	1.0 l
Energy kcal/100 ml	50	50
Osmolality	220	220

As elemental diets have been shown to cause micro-nutrient deficiency in patients suffering from prolonged sickness, a commercially prepared metabolite mixture containing multivitamins and essential minerals will be given to all patients daily for two weeks.

A disadvantage of using MCTs for longtime is the risk of developing

essential fatty acid (EFA) deficiency. To reduce this risk, safflower oil, a rich source of EFAs, will be applied topically during the period the patients are on study diets.

After recovery from diarrhoea, a transitional diet (half strength rice suzi) will be tried, and if tolerated, the patients will be sent home on this diet.

**Use of antibiotics :** Patients from whom cholera, shigella or salmonella are isolated on admission (stool culture reports will be available by 48 hours, i.e. before balance period starts) will be transferred from the study and treated with appropriate antibiotics. Patients having *E. histolytica* (haematogenous form) will not be included in the study and will be treated accordingly. Patients from whom *G. lamblia* or *E. histolytica* (cyst form) is isolated, or who have small intestinal bacterial overgrowth as found after culture of jejunal aspirate, will be treated with specific antimicrobials after the study period is finished. Only penicillin, which has got minimal effect upon enteric pathogens, may be used for mild infections during the study period.

**Management of patients who failed on study diets :** Antibiotics, if indicated as described above, will be given. Management of those patients who fail to respond will be tried by more dietary manipulation through elimination of different dietary components and maintaining parenteral hydration and nutrient support.

**Transfer from study :** Any child developing sepsis, convulsion, enterocolitis, pneumonia, or any other serious condition will be immediately transferred to the intensive care unit, and will be excluded from the study. Data upto the point of transfer or deviated course for intervention will be considered in analysis.

**Follow up :** To monitor the patients' prognosis and also to ensure proper dietary management, a weekly follow-up for first 2 weeks and then bi-weekly for another 6 weeks will be made. The patients' parents will be asked to come to the hospital for the follow-up check-ups. 6 weeks after discharge, trial with cow's milk test feed will be given during follow-up

visit and the patient observed for 6 hours. A repeat breath H2 test will be performed at the same time. If tolerated, then transition to normal milk-based home will be advised, otherwise milk-free diet will be continued.

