**Definations :**

1. Diarrhoea - passage of 4 or more liquid motions within 24 hours.
2. Persistent diarrhoea - diarrhoea persisting for more than 2 weeks following an episode of acute diarrhoea.
3. Cessation of diarrhoea - passage of soft stool or formed stool, and no liquid stool in 48 hours.
4. Dietary failure - patients in whom diarrhoea does not stop by 7 days after starting study diet.

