### Response Variables

1. Coefficient of absorption of fat, protein and carbohydrate.
2. Stool output (g/kg/24 hrs) over the study period
3. Duration of diarrhoea.
4. Weight gain (or loss) by day 7
5. Amount of I.V. needed (a proxy indicator of diarrhoeal severity)
6. Improvement in intestinal function as measured by intestinal mucosal permeability test
7. Proportion of success in each dietary group
8. Growth rate and morbidity during follow up

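### A randomised child transferred for serious illness before day 7 counts as neither failure nor recovery, and the rule for his data can distort the success proportion and the duration of diarrhoea.

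*Protocol*

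**What the plan says.** Children are randomised after a 24-hour baseline period and then start the study diet (General management). Under Balance study, the paragraph Transfer from study applies to "Any child developing sepsis, convulsion, enterocolitis, pneumonia, or any other serious condition". In that event the plan is that he "will be immediately transferred to the intensive care unit, and will be excluded from the study". On his data it adds: "Data upto the point of transfer or deviated course for intervention will be considered in analysis".

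The Definitions section gives two end states. One is "Dietary failure - patients in whom diarrhoea does not stop by 7 days after starting study diet". The other is "Cessation of diarrhoea - passage of soft stool or formed stool, and no liquid stool in 48 hours". Neither mentions transfer, serious complication or death.

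Response Variables lists "Proportion of success in each dietary group" and the duration of diarrhoea among eight outcomes, and the sample size is calculated on duration. Data analysis names chi-squared, t, rank and regression methods and none for censored times.

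A separate rule, under Use of antibiotics, applies to "Patients from whom cholera, shigella or salmonella are isolated on admission". These children also leave the study.

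**The concern.** The triggering events arise after allocation, and the diet could influence them; enterocolitis is the plainest case. Removing a child for such an event, or stopping his record there, makes the analysed set depend on an outcome that the trial should be measuring. The protocol defines no result for him in either of the two clinical outcomes concerned. At stake are the outcome that sizes the trial, the success proportion, and the visibility of serious illness on one diet. With about 25 children per arm, two or three transfers are enough to matter.

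**Working it through.** **Plan's own figure.** The inputs under Calculation of sample size are means of 3.75 and 4.91 days, SD 1.31, difference 1.15, multiplier 7.9 and correction 29/27. Then 2 × 1.31² × 7.9 / 1.15² = 20.50, and 20.50 × 29/27 = 22.02. The stated 22 per group reproduces and is not in dispute.

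**Applying the definitions.** Take a child transferred on diet day 2 who is still passing liquid stools. He has not reached 7 days, so the failure definition does not apply. He has not gone 48 hours without liquid stool, so the cessation definition does not apply. The transfer paragraph then allows two readings, and each causes a problem.

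**Reading 1: he is excluded.** Assume 25 per arm, 18 successes and 3 transfers. Counting all randomised children gives 18/25 = 72.0%; leaving out the transfers gives 18/22 = 81.8%. With 2 to 5 transfers the figure runs from 18/23 = 78.3% to 18/20 = 90.0%. For duration, suppose there is no true difference (mean 4.91, SD 1.31) and the 2 to 5 children with the longest durations are dropped from one arm. In 20,000 simulated trials that arm's mean falls by 0.20 to 0.44 day. It shows a significant advantage in 9% to 24% of trials, against a nominal 2.5%.

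**Reading 2: his time to transfer is used as his duration.** In the simulation (20,000 trials, 22 per arm, normal durations, SD 1.31, t test), a transferred child's duration becomes the smaller of his own time and a value drawn evenly from 0.5 to 3 days. The mean of that draw is 1.75 days, so a hand check is possible. A transferred child loses about 3.75 − 1.75 = 2.00 days on coconut oil and 4.91 − 1.75 = 3.16 days on soya oil.

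| Assumed transfers, coconut v soya | Hand check of the difference (days) | Simulated difference (days) | Power |
|---|---|---|---|
| none | 1.16 | 1.16 | 82% |
| 10% v 10% | 1.16 + 0.10×2.00 − 0.10×3.16 = 1.04 | 1.05 | 62% |
| 5% v 15% | 1.16 + 0.05×2.00 − 0.15×3.16 = 0.79 | 0.79 | 39% |
| 12% v 4% | 1.16 + 0.12×2.00 − 0.04×3.16 = 1.27 | 1.28 | 83% |

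With no true difference (both means 4.91), 12% v 4% creates an apparent gain of about (0.12 − 0.04) × 3.16 = 0.25 day for the arm with more transfers. That arm is falsely significant in about 7% of trials, against 2.5%. With 12% v 0% the chance is 12%, and with 20% v 0% it is 25%.

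**Effect of worst-rank handling.** With 25 per arm, no true difference, transfers unrelated to duration and 2 to 5 of them in one arm at day 2, using time to transfer gives a false advantage of 7% to 24%. Ranking those children worst in a Mann-Whitney test gives 0.4% or less.

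**The case against.** - The protocol does not state the denominator of the success proportion, nor that transfer ends the diarrhoea. Data kept to transfer could also be treated as censored. This stands. A reader might infer that the plan both drops these children from success and enters their transfer time as a duration. The documents fix neither; these are alternative readings. However, no method for censored times is listed, and the exclusion itself is written in the protocol rather than left to an analysis plan.
- A reader might infer that the rule always favours a harmful diet. It does so only if transfers are more frequent on that diet. Under the planned effect, 12% v 4% moves the difference only from 1.16 to 1.28 days and leaves power almost unchanged. The entry exclusions for severe infection, high fever and severe malnutrition should also keep transfers down.
- A reader might add the culture-based removals to the bias argument. Reports come after allocation ("stool culture reports will be available by 48 hours, i.e. before balance period starts"), so randomised children are lost. But the organism is isolated on admission, and the diet cannot affect that. Those removals cost numbers and do not favour the diet with more illness.
- Keeping every randomised child is impossible for the absorption coefficients, which need a completed 72-hour collection between markers. This stands, and it limits the remedy to success and duration.
- Duration and success are two of eight response variables, and none is named primary. True, but duration is the one on which the trial is sized.

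**Conclusion.** The point holds for the transfer rule together with the definitions of failure and cessation. A child transferred before day 7 with continuing diarrhoea has no defined result, and each natural reading either removes a poor outcome or makes it look like a good one. Where transfers are unequal and there is no true difference, an assumed 12% v 4% raises the chance of a false advantage for the arm with more transfers to about 7% against 2.5%. Where they are equal, an assumed 10% in each arm lowers power from 82% to 62%. All transfer rates, transfer times and success counts here are assumptions, because the protocol gives none. That the rule will favour a harmful diet, or that the culture-based removals bias the comparison, goes further than the documents support.

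**What to change.** Amend Transfer from study, the Definitions section and Data analysis so that, for the success proportion and the duration of diarrhoea:

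- every child randomised and started on a study diet stays in his allotted group, except children removed for a pathogen in the admission specimen, who are reported by arm;
- transfer for a serious condition, or death, before cessation counts as not a success;
- time to transfer is never used as a duration, and such a child takes the worst rank in a rank test;
- transfers are shown by arm and reason.

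Absorption coefficients stay limited to children with a completed balance collection, with the number missing shown by arm.

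The cost is wording, plus a record of date, reason and stool status at transfer. The downside is that duration becomes a rank-based composite, whereas the trial is sized on a difference in means. Worst ranks guard against the false advantage but should not be expected to restore power when transfers are equal. Clinical care before and after transfer is unchanged.

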**Definations :**

1. Diarrhoea - passage of 4 or more liquid motions within 24 hours.
2. Persistent diarrhoea - diarrhoea persisting for more than 2 weeks following an episode of acute diarrhoea.
3. Cessation of diarrhoea - passage of soft stool or formed stool, and no liquid stool in 48 hours.
4. Dietary failure - patients in whom diarrhoea does not stop by 7 days after starting study diet.

**STATISTICAL CALCULATION**

**Calculation of sample size**

Expecting the mean duration of diarrhoea with coconut oil based formula to be 3.75 days and that of soya oil based formula to be 4.91 days, the sample size is calculated based upon the formula.

$$\frac{2\sigma^2(Z_{\alpha/2} + Z_{\beta})^2}{\delta^2} \times (f+3)/(f+1)$$

Where  $\sigma^2$  = pooled variance

$\delta$  = difference between the means

and  $f$  = degrees of freedom

With the confidence limit of 95% and power of 80%,  $(Z_{\alpha/2} + Z_{\beta})^2 = 7.9$ .

Substituting the values, the calculated sample size is

$$\frac{2 \times 1.31^2 \times 7.9}{1.15^2} \times \frac{29}{27} = 22$$

or 44 patients for both groups.

With anticipation of refusals and dropouts, a total of 50 patients will be enrolled into the study.

### Data analysis

All data generated from the study will be entered into a microcomputer and appropriate statistical tests will be performed. The two study groups will be compared on admission and pre-randomisation data to assess their comparability. The response variables will be compared after evaluating the distribution so that appropriate tests could be applied. Chi-squared test, Student's 't' test, Mann-Whitney's 'U' test, Wilcoxon's Rank/Sum test and multiple regression analysis (keeping co-efficients of absorption of nutrients as the dependent variable) will be considered.

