#### General management

All hydration including initial hydration will be made by I.V. solutions during the entire study period. During the first 24 hours (baseline observation period), baseline data on stool output, vomitus, food intake, and requirement of I.V. fluids will be obtained, and stool output rate will be calculated. The diet during this period will be half strength milk formula. Breastfeeding will be continued and its intake will be measured.

The eligible patients will be randomly assigned to one of the two dietary groups. In the next 24 h, the patient will receive the study diet (pre-balance period). The oral intake will be restricted upto 200 ml/kg.d. All feed will be given hourly.

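### Pre-diet stool output and I.V. need are recorded for 24 hours but given no role in comparing the diets beyond a comparability check, so available precision is left unused

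*Protocol*

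**What the plan says.** Protocol, General management: in the first 24 hours, before random assignment and the study diet, "baseline data on stool output, vomitus, food intake, and requirement of I.V. fluids will be obtained, and stool output rate will be calculated". Stool output and the amount of I.V. fluid return as items 2 and 5 under Response Variables. Stool output there covers the study period as a whole; no time window is given for I.V. fluid.

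Protocol, Data analysis: the stated use of pre-treatment data is that "The two study groups will be compared on admission and pre-randomisation data to assess their comparability". The section then lists chi-squared, t, Mann-Whitney and Wilcoxon tests, and multiple regression with the absorption coefficients as dependent variable. These methods are to be considered once the distributions have been seen. No covariates are named.

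Protocol, Special investigations, on the lactulose/mannitol test: "This test will be performed on admission, and after 7 days to assess change in intestinal function". Response Variables item 6 is improvement on this test.

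On weight, Response Variables item 4 reads "Weight gain (or loss) by day 7", with no starting weight named. The schedule puts anthropometry on Days 1 and 8. General management adds: "All hydration including initial hydration will be made by I.V. solutions during the entire study period".

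**The concern.** For stool output and I.V. need, the trial holds a pre-diet value of the same quantity in the same child. This is usually the most useful covariate a trial can have, and the plan names no analysis that uses it to compare the diets. Looking at whether the groups are comparable leaves any chance difference in place. It also leaves between-child variation in purging in the error term.

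The outcome windows add to this. As worded, the pre-diet day could be counted inside stool output and I.V. volume, although the diet cannot have affected that day.

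Weight gain has a related gap. If it starts from a weight taken before I.V. rehydration, replaced water is counted as gain, by an amount that varies between children for reasons unrelated to diet.

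**Working it through.** **The plan's own figure.** Calculation of sample size begins: "Expecting the mean duration of diarrhoea with coconut oil based formula to be 3.75 days and that of soya oil based formula to be 4.91" (in days). With SD 1.31, difference 1.15 and multiplier 7.9, 2 × 1.31² × 7.9 / 1.15² = 20.50. Multiplied by 29/27 this is 22.02, stated as 22 per arm (44 in all, 50 enrolled). The means differ by 1.16, which gives 21.64, also 22. The figure reproduces. It concerns duration of diarrhoea, so this point does not touch it.

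**Chance imbalance.** The standard error of the between-arm difference in a baseline mean, in SD units, is √(2/n): √(2/22) = 0.30 and √(2/25) = 0.28. With a baseline-outcome correlation of 0.5 (assumed), an imbalance of 0.30 SD carries 0.5 × 0.30 = 0.15 SD into the unadjusted outcome difference.

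**Precision.** The documents give no correlation r, so r is an assumed range. For stool output and I.V. volume, ANCOVA leaves residual variance σ²(1 − r²) against σ² unadjusted. For permeability the comparator is the change score, with variance 2σ²(1 − r) if the variance is the same on both days. The ratio is (1 − r²) / [2(1 − r)] = (1 + r)/2.

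| r (assumed) | 1 − r² | Variance cut, ANCOVA vs unadjusted | 50/(1 − r²) | ANCOVA / change score, (1 + r)/2 |
|---|---|---|---|---|
| 0.3 | 0.91 | 9% | 55 | 0.65 |
| 0.5 | 0.75 | 25% | 67 | 0.75 |
| 0.7 | 0.51 | 49% | 98 | 0.85 |

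The fourth column is the number of children who, unadjusted, would give the precision of 50 with adjustment.

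Estimating the slope has a small cost. For a normal covariate and 22 per arm, the variance is multiplied on average by 1 + 1/(2n − 4) = 1 + 1/40 = 1.025. Adjustment therefore breaks even at r² = 1 − 1/1.025 = 0.024, or r of about 0.16.

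**Weight.** No fluid deficit or weight SD is given. Assume deficits spread evenly over 0–5% or 0–10% of a 6 kg child, that is 0–300 g or 0–600 g. The mean spurious gain is 150 g or 300 g, with SD 300/√12 = 87 g or 600/√12 = 173 g. Take an assumed true-gain SD of 150 to 250 g:

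- 0–5%: variance rises by (150² + 87²)/150² = 1.34 down to (250² + 87²)/250² = 1.12.
- 0–10%: the factor is 2.33 down to 1.48.

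The mean shift is expected equally in both randomised arms and cancels in the comparison. Only the spread matters.

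**The case against.** The strongest reply is that the section fixes little. Methods are only to be considered, and covariates are commonly left to a statistical analysis plan, which is not at hand. Part of this stands. But the section does state a use for pre-treatment data and ties regression to one family of outcomes, and stool output and I.V. volume are outside it. It is also true that an unadjusted comparison of randomised groups is valid, and that r is unknown. In addition, excluding children below 40 g/kg in the first 24 hours narrows the range of baseline stool output and may lower r.

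Four stronger readings are tempting but unsupported:

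- A reader might infer that all baseline data serve only the comparability check. Permeability is already assessed as change, baseline stool output also sets eligibility, and breast milk has its own intake columns in the balance sheet.
- A reader might infer that the Day 1 weight precedes rehydration. No section gives that order, and the balance sheet has a body-weight column for the balance days. What is missing is a definition.
- A reader might turn the variance gains into power using 1.15/1.31. That effect size belongs to duration of diarrhoea, which this change does not cover. No effect size or SD is given for the outcomes it does cover.
- A reader might infer that comparability will be judged by significance tests, or that breast-milk intake is left out of the absorption regression. The Protocol says neither. A main-effect covariate for breast milk would in any case not undo dilution of the oil contrast.

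**Conclusion.** The point holds as a minor efficiency improvement. For stool output and I.V. volume, the plan collects same-measure pre-diet values and names no analysis that uses them in the treatment comparison. The gain is 9% to 49% of residual variance for an assumed r of 0.3 to 0.7, less if the entry cut-off weakens r, and nil below about 0.16. For permeability the remaining gain is that of ANCOVA over a simple change: 0.65 to 0.85 of its variance over the same range, assuming equal variances on the two days. Separately, the starting weight is undefined. If it is a pre-rehydration weight, the result is added noise, not expected bias between arms. The sample size and every other stated figure are unaffected.

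**What to change.** In Data analysis, state that:

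- stool output (g/kg per 24 hours) and I.V. volume, both counted from the start of the study diet, will be compared by ANCOVA with the child's own first-24-hour value as covariate, on the log scale or by rank ANCOVA if skewed;
- the Day 8 log lactulose/mannitol ratio will be compared by ANCOVA on the Day 1 value, in place of a simple change.

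In Response Variables, name the starting weight for weight gain and its timing relative to initial I.V. hydration. A weight taken after rehydration, at the start of the study diet, is the better baseline.

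The cost is a few sentences, one degree of freedom per analysis and, if no such weight is already taken, one ward weighing. No more children are needed.
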